2.2 Data included in the analysis

All data reported in the database (scheduled, repeat and unscheduled visits) up to the cut-off date will be included in the analyses.

2.3 Analysis sets

The following analysis sets, or populations, will be considered in the data analyses:

Full analysis set (FAS) comprises all patients to whom study treatment has been assigned. Demographics, baseline characteristics, and patient disposition will be presented using the FAS. Furthermore, all efficacy data will be analyzed using the FAS.

The Safety set includes all patients who received at least one dose of study treatment. All safety data will be analyzed using the Safety Set.

2.4 Patients and treatments

2.4.1 Patient disposition

Patient disposition will be summarized using the Full analysis set (FAS). The following will be tabulated:

- Number (%) of patients screened;
- Number (%) of patients enrolled;
- Number (%) of patients, who remained in the trial at the time of data cut-off;
- Number (%) of patients who discontinued the treatment;
- Number (%) of patients with primary reason for end of treatment (based on patient status entered in the 'END OF TREATMENT DISPOSITION' page);
- Number (%) of patients with primary reason for end of study (based on completion of 'STUDY EVALUATION COMPLETION' page);

Listings will be provided for disposition, inclusion/exclusion criteria and the screening logs.

2.4.2 Patient demographics and other baseline characteristics

Demographic and other baseline data including disease characteristics will be summarized descriptively using the FAS. Demographic data will include age, age categories (≤ 60 , > 60 years), sex, race, ethnicity, weight, and height. Baseline characteristics will include polycythemia vera history including bone marrow biopsy, any prior medication for PV (yes/no), frequency of phlebotomy within 52 weeks prior to screening (1, 2, > 2), frequency of patients with thromboembolic events; frequency of patients with pre-malignant or non-melanoma malignant skin lesion (NMSC), HU resistance or intolerance, Hct ($< 45\%$, $\geq 45\% - \leq 50\%$, $> 50\%$), WBC counts [$(\leq 10, > 10 - \leq 15, > 15) \times 10^9/L$] and platelet counts at baseline [$(< 100, \geq 100 - < 400, \geq 400 - < 600, \geq 600) \times 10^9/L$]. Baseline characteristics will also include

splenectomy history due to PV (yes/ no); previously treated with ruxolitinib (yes/no) and patient received ruxolitinib on a clinical trial (yes/no), palpable spleen at screening (yes/no and Eastern Cooperative Oncology Group (ECOG) Performance Status (0, 1, 2).

Listings including smoking history will be provided using FAS.

2.4.3 Protocol deviations

Protocol deviations will be categorized into the following categories per ICH guidelines for CSR-reportable protocol deviations:

- Patient developed study/treatment withdrawal criteria during the study, but was not withdrawn
- Patient received the wrong treatment or incorrect dose
- Patient took an excluded concomitant medication
- Patient did not satisfy the entry criteria

Other important deviations may also be identified and summarized, as necessary, which may impact the scientific value of the trial.

All protocol deviations, including protocol deviations leading to exclusion from any analysis population will be specified in the study Validation and Planning (VAP) document.

The number and percentage of patients in the Full Analysis Set (FAS) with any protocol deviation will be tabulated by the CSR-reportable deviation categories.

All protocol deviations will be listed using FAS.

2.4.4 Antineoplastic therapy

Prior antineoplastic medications for hematologic disease, including PV, will be listed and summarized by preferred terms using the FAS. Duration of prior antineoplastic use will be summarized descriptively. The reason for discontinuation of therapy will also be summarized categorically.

All data related to prior antineoplastic medication will be listed by patients using FAS.

2.4.5 Date of first/last administration of study drug

The start date of study drug is defined as the first date when a non-zero dose of study drug was administered and recorded on the Dosage Administration Record (DAR) eCRF.

The date of last administration of study drug is defined as the last date when a non-zero dose of study drug was administered and recorded on DAR eCRF.

2.4.6 Extent of exposure

All exposure analyses will be performed on Safety set.

2.4.6.1 Dose intensity and exposure

Definitions of duration of exposure, cumulative dose, average daily dose, actual dose intensity (DI), planned dose intensity (PDI), relative dose intensity (RDI), percentage of days dosed, percentage of days the planned/intended dose was received, as well as intermediate calculations, include:

- Duration of exposure (days): last date of study drug – first date of study drug + 1
- Cumulative dose (mg): total dose of study drug taken by a patient in the study
- Number of dosing days (days): duration of exposure – number of zero dose days
- % Days dosed: $100 \times \text{number of dosing days} / \text{duration of exposure (days)}$
- % Days with planned dose: $100 \times \text{number of days with planned dose} / \text{duration of exposure (days)}$
- Average daily dose (mg/day): cumulative dose (mg) / number of dosing days (days)
- DI (mg/day): cumulative dose (mg) / duration of exposure (days)
- PDI (mg/day): cumulative planned dose (mg) / duration of exposure (day)
- RDI (%): $100 \times \text{DI (mg/day)} / \text{PDI (mg/day)}$

Duration of exposure to study drug, actual cumulative dose, percentage of actual days dosed, percentage of days the planned dose was received, average daily dose, DI and RDI (including categories: <70, 70-90, >90) will be summarized descriptively. In addition, the duration of exposure to study drug will be categorized into time intervals; frequency counts and percentages of patients with exposure in each time interval will be presented.

The derived parameters above will also be listed using Safety set.

2.4.6.2 Dose changes

The number and percentage of patients with dose interruption, reduction and increase will be summarized in the safety set. Dose interruption, reduction and increase are defined as follows:

- **Interruption** is defined as any period of zero total daily dose followed by a non-zero dose.
- **Reduction** is defined as any decrease from the immediate prior non-zero total daily dose. Zero daily doses are not regarded as reductions.
- **Increase** is defined as any increase from the immediate prior non-zero total daily dose.

The number and percentage of patients with dose interruption, reduction and increase, along with reasons for dose change or dose delay will be summarized using Safety set.

The duration of dose changes (days) will be summarized.

Listings of all doses of the study drug along with dose reduction, increase and interruption and reasons for dose change or dose delay will be presented. The derived parameters above will also be listed using Safety set.

2.4.7 Concomitant Medications

Concomitant medications and significant non-drug therapies after the start of the study treatment and up to 30 days after the last dose date will be summarized by ATC code the Safety Set. These summaries will include medications starting on or after the start of study treatment or medications starting prior to the start of study treatment. All concomitant medications and significant non-drug therapies will be listed using Safety set, including any prior medications and significant non-drug therapies starting and ending prior to the start of study treatment.

2.5 Analysis for the primary objective

The primary objective is to evaluate safety data in patients with PV who are hydroxyurea-resistant or -intolerant. The safety set will be used for the analysis of clinical safety data.

2.5.1 Variable

Refer to section 2.8.1.

2.5.2 Statistical hypothesis, model and method of analysis

No statistical hypotheses will be tested in this ETP.

2.5.3 Handling of missing values

Missing/partial dates for prior anti-neoplastic therapy, adverse event, death and dosing record will be imputed. Details imputation rules for missing dates are described in section 4.4.

2.6 Analysis of the key secondary objective

Not applicable.

2.7 Analysis of the secondary efficacy objectives

2.7.1 Analysis for secondary efficacy objectives

There will be three secondary efficacy endpoints (i-iii). All three endpoints will be summarized descriptively by visit using the FAS. No formal statistical hypotheses will be tested.

- i. Change in Hct levels from Baseline to each visit
- ii. Change in spleen length from Baseline to each visit
- iii. Change in MPN-SAF TSS score from Baseline to each visit

In addition to change from baseline analyses, descriptive statistics by visit in terms of n, mean, median, SD (standard deviation), min and max will also be provided for each of the secondary efficacy variables. Patients with an evaluable baseline score and at least one evaluable post

baseline score during the treatment period will be included in the change from baseline analyses. In addition to the secondary efficacy objectives, number of phlebotomies patients received since their last visit will be summarized by visit.

A listing for each secondary variable will also be provided by patient using FAS.

2.7.1.1 Handling of missing values

No imputation will be applied for missing value.

2.7.2 Patient-reported outcomes

The MPN-SAF TSS will be used to collect data on the patient's disease-related symptoms. No formal statistical test will be performed. The details on the questionnaire as well as the derivation of raw and standardized scores are provided.

Patients with an evaluable baseline score and at least one evaluable post baseline score during the treatment period will be included in the change from baseline analyses. Missing data items in a scale will be handled based on the instrument manual. No imputation will be applied if the total or subscale scores are missing at a visit.

2.7.3 Biomarkers

Not applicable

2.7.4 Resource utilization

Not applicable

2.8 Safety evaluation

The overall observation period will be divided into mutually exclusive segments:

We have

1. pre-treatment period: from day of patient's informed consent to the day before first dose of study medication
2. on-treatment period: from day of first dose of study medication to 30 days after last dose of study medication
3. If applicable, post-treatment period: starting at day 31 after last dose of study medication.

2.8.1 Adverse events

Adverse events (AE) will be coded using the MedDRA dictionary that provides the system organ class and preferred term information. CTCAE version 4.03 or higher will be used for reporting AE severity. Treatment-emergent AEs starting on or after the date of first study medication (including AEs that start within 30 days after the discontinuation of the study medication) will be reported.

All AE will be summarized (frequency counts and percentages) by system organ class and/or preferred term, and maximum severity grades, except where otherwise noted. A patient with

multiple CTC grades for an AE will be summarized under the maximum CTC grade recorded for the event.

The following selection of AEs will be listed and summarized separately using Safety set. All these AEs will be summarized for all grades and for grade 3 or 4 side-by-side.

- AEs regardless of study drug related
- AEs suspected to be study drug related
- On-treatment deaths, by primary system organ class and preferred term
- All deaths, by primary system organ class and preferred term
- SAEs regardless of study drug relationship
- SAEs suspected to be study drug related
- AEs leading to discontinuation of study drug
- AEs leading to discontinuation of study drug that are suspected to be study drug related
- AEs requiring dose adjustment or study drug interruption
- AEs requiring concomitant medication or non-drug therapy.
- Adverse events which are not serious adverse events, regardless of study drug relationship
- AEs of Specific safety event categories (SEC)
- SAEs adjusted for patient-year exposure, regardless of study drug relationship

Specific safety event categories (SECs) include hematopoietic thrombocytopenia (SMQ), hematopoietic erythropenia (SMQ) and hematopoietic leukopenia (SMQ), hemorrhage (SMQ) and infections (SOC). The naming of SMQs and grouping of preferred terms into corresponding SMQs will be based on the MedDRA version 17.0 or higher. When discussing these SECs in the CSR, the clinical review will be undertaken to ensure the correct interpretation on the analysis results based on SMQs.

The number (%) of patients with specific safety event categories will be summarized using the Safety set. Exposure (patient-years)-adjusted summaries will also be generated for these specific safety event categories.

Deaths which occurred during the study treatment or within 30 days after discontinuation of the study treatment will be listed and Safety set will be used. All deaths will also be listed using Safety set.

Note that patients will be discontinued from the study if dose is interrupted more than 8 weeks due to AE.

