10.5.3.2 Adverse events (AEs)

Summary tables for adverse events (AEs) have to include only AEs that started or worsened during the on-treatment period, the ***treatment-emergent*** AEs. However, all safety data (including those from the pre and post-treatment periods) will be listed and those collected during the pre-treatment and post-treatment period are to be flagged.

The incidence of treatment-emergent adverse events (new or worsening from baseline) will be summarized by system organ class and or preferred term, severity (based on CTCAE grades), and type of adverse event.

Deaths reportable as SAEs and non-fatal serious adverse events will be listed by patient and tabulated by type of adverse event.

Specific safety event categories (SEC) will be considered. Such categories consist of one or more well-defined safety events which are similar in nature and for which there is a specific clinical interest in connection with the study treatment(s).

For each specified SEC, number and percentage of patients with at least one event part of the SEC will be reported.

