2.1 CSR Section 9.7.1 Statistical and analytical plans

The statistical analysis of these data will be performed by Novartis personnel in accordance with the data analysis section, Section 10, of the study protocol which is available in [Appendix 16.1.1 of the CSR](#). Important information is given in the following sections and details are provided, as applicable, in [Appendix 16.1.9 of the CSR](#). SAS version 9.4 will be used in all analyses.

This is a global, single arm, open-label, multi-center trial designed to provide early access and evaluate the safety of ruxolitinib in patients with polycythemia vera who are HU resistant or intolerant and who have no other standard treatment options. Efficacy and patient reported outcomes will also be assessed.

Final analyses will be performed when all patients have been followed for 30 days after they have either prematurely discontinued or been discontinued from the study after completing treatment as per protocol (i.e., until the drug is commercially available for this indication in each participating country).

It is planned that the data from all centers that participate in this trial will be pooled and analyzed. Unless otherwise specified, qualitative data will be described using frequency and percentages, while quantitative data, will be described using descriptive statistics: n, mean, standard deviation, median, minimum, and maximum.

No interim analysis is planned, and the final analysis will be performed after all patients have either completed the study or have been prematurely discontinued from the study.

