4.3 Safety evaluations

The text below gives more detailed instructions and rules needed for programming of the analyses described in [Section 2.8.1](#).

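### SAP 2.8.1 selects treatment-emergent AEs by start date only, while protocol 10.5.3.2 also counts AEs that worsened on treatment

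*SAP*

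**What the plan says.** **Protocol.** Section 10.5.3.2 says AE summary tables "have to include only AEs that started or worsened during the on-treatment period". Its next paragraph repeats the criterion: "The incidence of treatment-emergent adverse events (new or worsening from baseline) will be summarized". Worsening has the same standing as new onset. The same section adds that all safety data "will be listed and those collected during the pre-treatment and post-treatment period are to be flagged".

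**SAP.** For the primary variable, SAP 2.5.1 says only "Refer to section 2.8.1". That section reports "Treatment-emergent AEs starting on or after the date of first study medication", with the addition "including AEs that start within 30 days after the discontinuation of the study medication". Both ends of the window are therefore set by when the event started. Two other places bear on the point. SAP 2.1 says in general that the analysis will be done "in accordance with the data analysis section, Section 10, of the study protocol". SAP 4.3 says that its text "gives more detailed instructions and rules needed for programming of the analyses described in" Section 2.8.1.

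**The concern.** The SAP uses the protocol's term, treatment-emergent, but attaches a narrower rule to it. A programmer who follows SAP 2.8.1 literally drops an event that began before first dose and became severe on drug. One who follows the protocol keeps it.

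The tables affected carry the primary objective. Protocol Table 3-1 names AEs, Grade 3 and 4 AEs, SAEs and AEs leading to discontinuation as primary endpoints. In a single-arm study with no hypothesis test, those counts are the main result. Hematology and vital signs have shift tables against baseline (SAP 2.8.2 and 2.8.4), so worsening there would show in another way. Infections and hemorrhage, both specific safety event categories in SAP 2.8.1, have no such table.

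**Working it through.** There is no planned figure to reproduce. The check sets the two rules side by side and traces single cases through them.

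**1. Does anything specific in the SAP restore worsening?**
- SAP 4.3 announces programming rules for 2.8.1. Its subsections cover baseline and multiple post-baseline assessments. Neither has a rule for a worsened AE.
- SAP 4.4.1 places an AE with a partial date before or after treatment start by its start date alone. No date of worsening is used.
- The maximum-grade rule in SAP 2.8.1 applies to AEs already selected, so it never reaches one that started before first dose.

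**2. Which events are exposed?**
- Under protocol 8.1.1, conditions present at consent go to Medical History, and their later worsening is itself an AE. If that AE is dated from the worsening, both rules count it when it falls on treatment.
- AEs are collected from consent, and screening may last 35 days (protocol 7.1.1). An AE that begins in that interval has a start date before first dose.
- If such an AE worsens on drug, the outcome depends on how it was recorded. Protocol 8.1.1 points both ways: it counts worsening of an existing condition as an AE, which suggests a new record, and it asks that a detected AE be followed for changes in severity, which suggests one record.

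**3. Case trace, one patient and one AE term**

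| Case | SAP 2.8.1 (start date only) | Protocol 10.5.3.2 (started or worsened) |
|---|---|---|
| A. Screening Grade 1, on-drug Grade 3, one record | Not counted | Counted, maximum Grade 3 |
| B. As A, plus a separate on-drug onset at Grade 1 | Counted, maximum Grade 1; not in Grade 3/4 | Counted, maximum Grade 3 |
| C. As A, plus a separate on-drug onset at Grade 2 | Counted, maximum Grade 2; not in Grade 3/4 | Counted, maximum Grade 3 |
| D. New record opened when the event worsened | Counted, maximum Grade 3 | Counted, maximum Grade 3 |

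In case D nothing is lost. Cases B and C show that another on-drug onset of the same term does not repair the loss: the patient stays in the all-grades count but drops out of Grade 3/4. A table of AEs leading to discontinuation can lose a patient in the same way.

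**4. Scale of one lost patient (not an estimate of how many)**
- Planned sample of about 500 (SAP 2.9.1): 1/500 = 0.20 percentage points.
- 65 patients enrolled when protocol Amendment 1 was written: 1/65 = 1.54 percentage points.

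The 65 is a count from mid-enrollment, not an analysis denominator. SAP 2.9.1 says the final number may differ from plan. The lower bound of the loss is zero, and the documents give no basis for an upper bound.

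**The case against.** The case on the other side has five parts.

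- **The SAP defers to the protocol.** SAP 2.1 invokes protocol Section 10, and the term treatment-emergent is defined there, so the SAP sentence may be shorthand. That is a possible reading, but a general pointer does not override a specific, narrower rule in the operative section. The authors did not rely on the pointer elsewhere: SAP Amendment 1 edited sections 2.4.7, 2.8 and 2.9.1 expressly to match the protocol.
- **Records may already be split.** Protocol 8.1.1 asks for one severity grade and one pair of dates per event, and SAP 2.8.1 expects a patient to have several grades for one AE. Both fit a separate record per grade. The second also fits repeat episodes, and neither settles what sites did.
- **The exposed group is small.** Exclusion 6 bars active infection that needs therapy, exclusion 12 bars significant uncontrolled conditions, and inclusion 5 requires recovery or stabilization from earlier drug reactions. This narrows the group and weakens infection as an example. A mild, untreated event that starts in screening and worsens on drug is still possible.
- **Other outputs would show the harm.** Pre-treatment events are listed and flagged, deaths are selected by date of death, dose changes are summarized with reasons, discontinuations count in disposition by primary reason, and three of the five safety categories are cytopenias covered by hematology shift tables. All true. None puts the event into the AE, SAE or Grade 3/4 tables under its own term.
- **The fix may recover little.** If the single record holds no dated grade change, no program can show that the worsening came after first dose. This stands, and the fix has to allow for it.

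**Conclusion.** The conflict holds. The SAP rule for the primary safety tables is narrower than the protocol's, and the difference can remove a patient from Grade 3/4, SAE or discontinuation counts. Confidence is high for the difference between the documents. The effect on results is unknown: it is zero if every worsening opened a new record, and otherwise cannot be estimated. The loss requires that an AE began between consent and first dose, worsened on drug, and was kept as one record with its original start date. No hypothesis test or decision threshold depends on these rows, but they are what the study reports. The point should be fixed, though it is not a flaw in the design.

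**What to change.** Replace the selection sentence in SAP 2.8.1 with wording such as:

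> *An AE is treatment-emergent if it started, or worsened in severity, between the date of first dose and 30 days after the last dose. Severity means CTCAE grade or, where none exists, the severity scale in protocol 8.1.1.*

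Then add two rules:
- State how worsening of an AE already present at first dose is identified in the records collected. SAP Amendment 1 is dated 13-Mar-2018 and the protocol's latest end date is 31 December 2017, so the rule must work on existing data.
- Where worsening cannot be dated relative to first dose, report the number of such AEs.

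The cost is one definition and, where grade changes are dated, a few lines of programming. Where they are not dated, the gain is limited to the reported count. The number of patients with any event in a table can only stay the same or rise. Maximum-grade rows may shift: in case C, one patient moves from the Grade 2 row to the Grade 3 row.

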2.5 Rationale for choice of comparators drugs

Not applicable.

3 Objectives and endpoints

Objectives and related endpoints are described in Table 3-1 below.

Table 3-1 Objectives and related endpoints

| Objective | Endpoint | Analysis |
|---|---|---|
| Primary | | Refer to Section 10.4 |
| To evaluate the safety of ruxolitinib | AEs, Grade 3&4 AEs & SAEs, events of special interest, AEs leading to discontinuation, and deaths. Evaluate changes in hematology." | |
| Secondary | | |
| Efficacy | Change in Hct levels from Baseline to each visit where measured | Refer to Section 10.5.2 |
| To evaluate change in hematocrit levels | Change in spleen length from Baseline to each visit where measured. | |
| Patient Reported Outcome | Change in MPN-SAF TSS score from baseline to each visit where measured. | Refer to Section 10.5.6 |
| To evaluate change in MPN-SAF TSS score | | |

4 Study design

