4.1 Description of study design

This is a global, single arm, open-label, multi-center protocol designed to provide early access and evaluate the safety of ruxolitinib in patients with polycythemia vera who are HU resistant or intolerant and who have no other standard treatment options. Efficacy and patient reported outcomes will also be assessed.

There are limited therapeutic options in this disease setting. Ruxolitinib will be provided until it becomes commercially available for this indication in each participating country or until 31 December 2017, whichever date occurs first.

Screening/baseline phase

- Screening/baseline assessments will be performed within 35 days prior to the first dose of ruxolitinib treatment (e.g., labs including hematology, blood chemistry, urine, and pregnancy tests, physical examination including spleen palpation, vital signs, and ECOG Performance Status).
- If all screening lab assessments are received, reviewed, and within protocol parameters and patient meets all inclusion and none of the exclusion criteria, the screening labs may be used as baseline and patient may continue to Day 1 within 14 days of the screen after the eligibility checklist has been completed in the IRT system.

Treatment phase/duration of treatment

- Patients who are eligible will receive ruxolitinib at a starting dose of 10 mg bid (see [Sections 6.3.4](#) and [Section 6.3.7](#) for exceptions). The first dose of ruxolitinib treatment is

administered on Day 1. Patients will have clinic visits every 4 weeks until Week 24 and every 12 weeks thereafter. The dose of drug may be adjusted during the study based on efficacy and safety to a maximum of 25mg bid (see [Sections 6.3](#) for guidance). Clinical suspicion of disease progression to MF, MDS, or AML (see [Appendix 4](#) and [Appendix 5](#) for definitions) or the occurrence of a Grade 3 or 4 events at any time requires a physical examination to assess disease status. This examination is to be performed promptly rather than waiting for the next scheduled visit.

- Patients may continue to receive ruxolitinib treatment until disease progression, (see [Appendix 4](#) and [Appendix 5](#)), as determined by the local investigator, unacceptable toxicity, death, withdrawal of consent for protocol specified procedures, or discontinuation from the treatment for any other reason until the drug becomes commercially available in each participating country or until 31 December 2017, whichever occurs first.

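### Most primary AE endpoints are planned only as crude percentages, over an on-treatment window that has no common length

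*SAP*

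**What the plan says.** Protocol Table 3-1 gives safety as the primary objective and lists the AE-type endpoints as "AEs, Grade 3&4 AEs & SAEs, events of special interest, AEs leading to discontinuation, and deaths", together with changes in hematology.

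SAP 2.8.1 sets the default measure, unless it states otherwise: "All AE will be summarized (frequency counts and percentages) by system organ class and/or preferred term, and maximum severity grades". Two exceptions that account for exposure follow in the same section. One is an item in its list of tables, "SAEs adjusted for patient-year exposure, regardless of study drug relationship". The other concerns the SECs (three cytopenia SMQs, hemorrhage and infections): "Exposure (patient-years)-adjusted summaries will also be generated for these specific safety event categories".

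On length of treatment, Protocol 4.1 says "Ruxolitinib will be provided until it becomes commercially available for this indication in each participating country or until 31 December 2017", whichever is first. Protocol 4.3, 6.1.5 and 7.1.3.1 instead put the end three months after local availability, with the same calendar cap. Protocol 6.1.5 adds patient-level reasons: progression, toxicity, new anti-cancer therapy, pregnancy, investigator or patient choice, loss to follow-up and death. SAP 2.8 defines the on-treatment period as running from first dose to 30 days after last dose. SAP 2.4.6.1 summarizes duration of exposure separately, also by time interval.

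**The concern.** A crude percentage answers a clear question when all patients are observed for about the same time. Here they are not. Part of the variation is administrative: it depends on the country's availability date and on how long before that date, or before the 2017 cap, the patient entered. The protocol itself indicates that availability was staggered. Section 1.2.1 reports approval in more than 45 countries with review continuing elsewhere, and the amendment summary says that some countries declined to take part because approval came earlier.

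Two groups of patients with the same underlying rate would show different percentages if one had been treated longer. A reader who sets these percentages beside other ruxolitinib data could take a difference in follow-up for a difference in safety. The plan provides a measure that accounts for exposure for some primary endpoints but not for others.

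**Working it through.** **Step 1: endpoints against planned outputs.** From Table 3-1 and SAP 2.8.1:

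| Primary AE endpoint | Crude % | Patient-year-adjusted |
|---|---|---|
| All AEs | yes | no |
| Grade 3/4 AEs | yes | only where serious or in an SEC |
| SAEs | yes | yes |
| Events of special interest (SECs) | yes | yes |
| AEs leading to discontinuation | yes | no |
| Deaths | yes | no separate line |

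Four of six have no adjusted summary of their own. No cumulative incidence or fixed-window incidence is planned for them either.

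**Step 2: how far a crude percentage moves with treatment length.** The documents give no event rates for planning and no follow-up distribution, so rates and durations here are assumptions. The sample size of about 500 is not statistically derived, so there is no planned figure to reproduce.

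Formula: crude proportion = 1 − exp(−rate × (T + 30/365.25)), where T is years of treatment and 30/365.25 = 0.0821 years is the tail in the on-treatment window. It takes a constant rate and observation over the whole window.

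At 0.2 per patient-year:
- T = 0.25: 1 − exp(−0.2 × 0.3321) = 6.4%
- T = 1: 1 − exp(−0.2 × 1.0821) = 19.5%
- T = 2: 1 − exp(−0.2 × 2.0821) = 34.1%

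The ratio of last to first is about 5.3. Over a range of assumed rates (ratios from unrounded values):

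| Rate per patient-year | T = 0.25 | T = 1 | T = 2 | Ratio, 2 to 0.25 years |
|---|---|---|---|---|
| 0.05 | 1.6% | 5.3% | 9.9% | 6.0 |
| 0.1 | 3.3% | 10.3% | 18.8% | 5.8 |
| 0.2 | 6.4% | 19.5% | 34.1% | 5.3 |
| 0.3 | 9.5% | 27.7% | 46.5% | 4.9 |
| 0.5 | 15.3% | 41.8% | 64.7% | 4.2 |
| 1.0 | 28.3% | 66.1% | 87.5% | 3.1 |

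**Step 3: the pooled figure.** The trial reports one percentage over all centers. Suppose that patients are treated for either 0.25 or 2 years, at 0.2 per patient-year:
- 20% short: 0.2 × 6.4 + 0.8 × 34.1 = 28.5%
- 50% short: 0.5 × 6.4 + 0.5 × 34.1 = 20.2%
- 80% short: 0.8 × 6.4 + 0.2 × 34.1 = 12.0%

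(Results use unrounded inputs.) The range is about 2.4-fold, and it needs a large swing in the mix.

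**Step 4: reading it backwards.** Rate = −ln(1 − 0.20) / (T + 0.0821). A crude 20% corresponds to 67.2 per 100 patient-years if treatment lasted 0.25 years, 20.6 if 1 year and 10.7 if 2 years.

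**The case against.** The strongest reply is that much of the gap is already covered.

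- A fatal event is an SAE by Protocol 8.2.1, so it falls within the adjusted SAE table. The SAP amendment log describes that table as broken down by maximum grade, so serious Grade 3/4 events are adjusted as well.
- The SECs take in cytopenias, and anemia and thrombocytopenia were the two most frequent events in the earlier PV study (73.5% and 32.4%, Protocol 1.2.1.3.2).

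This stands, and it narrows the point. What remains is mainly non-serious events outside the SECs, AEs leading to discontinuation, and a separate line for deaths. Protocol 8.1.1 does not use CTCAE Grade 5, so the grade columns of the SAE table would not isolate deaths.

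A second reply is that a reader can multiply mean exposure by N and divide. That works for rare events. At 0.05 per patient-year over 2 years, 9.9 / 2.0821 gives about 4.7 per 100 patient-years against a true 5. It fails for common ones: at 1.0 per patient-year, 87.5 / 2.0821 gives about 42 against 100, because person-time should stop at the first event.

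A third reply is that patient-year rates assume a roughly constant hazard and say little for an endpoint that nearly every patient reaches. That also stands. It is why the crude percentages should stay and why the rates are most useful by preferred term.

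Some stronger readings are tempting but not supported:
- A reader might infer that the percentages have no time base at all. SAP 2.8 defines one; it is just not of common length.
- A reader might infer that launch dates drive the results as much as the drug does. The documents give no launch dates or follow-up distribution, and launch is only one of several reasons for stopping.
- Leaving out the 30-day tail gives 4.9% to 33.0% at 0.2 per patient-year, nearly sevenfold. That is not the window the SAP counts over.
- Adding the SAE table might be read as the sponsor conceding the principle. The amendment log says only that the table was newly added to the table shells.

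**Conclusion.** The point holds in a limited form and merits a change. Four of the six primary AE endpoints have no exposure-adjusted summary of their own, although time at risk differs between patients, partly for administrative reasons. At an assumed constant 0.2 per patient-year, the crude percentage varies about 5.3-fold between 0.25 and 2 years of treatment; over assumed rates of 0.05 to 1.0, the range is about 6.0-fold to 3.1-fold. The pooled percentage would vary less, about 2.4-fold in the two-group illustration. All of these sizes rest on assumed rates and durations.

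No test or error rate is affected: the trial is single-arm and descriptive, tests no hypothesis, and plans no between-country comparison. The harm is to the interpretation of the primary safety results and to their comparison with other data.

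**What to change.** In SAP 2.8.1, extend the patient-year-adjusted summary already planned for SAEs and SECs to all AEs by preferred term, Grade 3/4 AEs, AEs leading to discontinuation, and on-treatment deaths. Place it beside the crude percentages, which stay.

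Define the measure as patients with an event per 100 patient-years. Person-time runs from first dose to first event or, if there is none, to the end of the on-treatment window: last dose plus 30 days, or death or data cut-off if earlier. State the same definition for the SAE and SEC tables, since SAP 2.8.1 does not give one.

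Separately, Protocol 4.1 and 7.1.2 (treatment until local availability) need to be reconciled with 4.3, 6.1.5 and 7.1.3.1 (three months after it), because this date shapes the exposure being summarized.

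The cost is longer tables and some extra programming on outputs of a kind already planned. No data collection changes. The rates need a note that they assume a roughly constant hazard.
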